6.2.1 Part I, Oral HPV Screening

Patient Enrollment and Screening (Visit 1, Day 0)

Location: Dental practitioner's office or clinic

1. Verify eligibility via web application;
2. Obtain consent via web application (Appendix A);
3. Administer electronic oral HPV risk factor survey via web application (Appendix C).
 - a. If patient is **not selected** by the web-application for oral rinse sample (approximately 64.1% of patients), a practice staff member will notify the patient that his or her **involvement in the study is complete**.
 - b. If patient is **selected** by the web-application for oral rinse sample (approximately 35.9% of patients); **continue through Visit 1, steps 4-5**.
4. Obtain participant contact information via web application;
5. Obtain oral rinse sample (done by dentist, dental hygienist or dental assistant); oral rinse samples are stored at 4°C, then shipped in batches to study laboratory by practice staff approximately once or twice a week.
6. Once the patient's oral rinse sample is received by the HPV detection laboratory (Polaris Innovation Centre), results will be communicated to dental practitioners within approximately 5 business days via the secure web application.
 - a. If patient has a **negative** high-risk oral HPV test result (anticipated to be approximately 33.4% of patients), proceed to **Visit 2A**; or
 - b. If a patient has an oral rinse sample that is not evaluable, proceed to **Visit 2B**; or
 - c. If patient has a **positive** high-risk oral HPV test result (anticipated to be approximately 2.5% of patients), proceed to **Visit 2C**.

HR-HPV Results Notification – Negative (Visit 2A: Day 14, -11 days to +5 business days)

Location: Telephone

1. Using an approved script (Appendix E), the dentist notifies the patient of their negative high-risk oral HPV test result and explains that their involvement in the study is now complete.

HR-HPV Results Notification – Not Evaluable (Visit 2B: Day 14, -11 days to +5 business days)

Location: Telephone

1. Using an approved script (Appendix G), the dentist notifies the patient that their oral rinse was deemed “not evaluable” by the study laboratory and the high-risk oral HPV test could not be conducted.
2. The caller will then invite the patient to schedule a visit at the dental office to recollect the oral rinse sample that can be sent for evaluation of high-risk HPV.

HR-HPV Results Notification – Positive (Visit 2C: Day 14, -11 days to +5 business days)

Location: Telephone

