11.1 Study Hypotheses

This pilot study is designed to test the following hypotheses:

- (1) The proportion of the high-risk HPV infection among individuals selected for oral rinse collection will be similar to the proportion predicted by the risk factor model;
- (2) Baseline study procedures will be feasible and acceptable to dental practice staff and patients;
- (3) The distribution of demographic and behavioral risk factors in the study population will be similar to the US population; and
- (4) Participants will be compliant with follow-up study procedures, including the blood draw, oral cancer screening examination, second oral rinse specimen collection and detailed oral cancer risk factor survey (Appendix J); and
- (5) Arranging and conducting the procedures will be feasible for RC and dental practice staff.

The study will determine whether or not oral HPV detection can be used to identify individuals in a dental practice who are at high-risk for HPV-associated oral cancer and who should be targeted for referral and screening for oral cancer.

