11.2 Sample Size Considerations

The sample size for this pilot study is based upon a dichotomous outcome in which participating patients are categorized as low-risk versus high-risk for oral high-risk HPV infection. Based upon our risk model derived from 5,500 individuals who are representative of the US population (NHANES), we expect 30% of the study population to be categorized as high-risk. A two-sided test of proportions with a type 1 error of 0.05 indicates that a pilot study with 1,000 individuals will have 90% power to detect a 5% or greater difference in the proportion of the study population that is categorized as high-risk. The ability to enroll a sample size of 1,000 will also provide assurance that a study with a large sample size is feasible in the National Dental PBRN.

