11.3 Final Analysis Plan

To accomplish the primary objective, our outcomes of interest will be the number of individuals determined to be in the top three deciles of risk based on our model (i.e., those selected for oral sample collection based on risk) as well as the proportion of those individuals with an oral high-risk HPV infection. Based upon our model in NHANES, we would expect that 30% of the participating population would be selected for specimen collection and that the resulting population would have an oral high-risk prevalence of 8.43% (95%CI 6.68% to 10.14%). The number of individuals selected as high-risk will be informative with regard to the distribution of

risk factors in the study population, and the proportion positive will be informative with regard to the β -estimates for our risk model.

Shown in the table below are the upper and lower bounds of the 95% CI for the proportion positive for oral high-risk HPV infection, assuming a range of 10-50% of the study population is categorized as high-risk based on our model. A proportion of the study population with oral high-risk infection that falls within the confidence bounds in the table below, given the sample size, will indicate that the β -estimates in our NHANES model are reasonable estimates of risk to the study population.

Sample size	Proportion	95% Confidence Interval	
		Lower Bound	Upper Bound
100	8.43%	2.98%	13.88%
200	8.43%	4.58%	12.28%
300	8.43%	5.29%	11.57%
400	8.43%	5.71%	11.15%
500	8.43%	5.99%	10.87%

To accomplish secondary objectives (1) and (3) a brief Provider Survey (Appendix P) will be administered via tablet computer/web-application to providers at each participating practice to assess acceptability of each procedure and willingness to participate in a future larger study. Results will be reported as summary statistics.

Descriptive statistics for secondary objective (3) include the proportion of individuals with high-risk oral HPV infection who:

- (1) Enroll in the follow-up study;
- (2) Attend a 6-month follow-up;
- (3) Provide blood serum sample; and
- (4) Provide second oral rinse.

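### Section 11.3 names the wrong denominator for its check of the risk model, and reads a result inside a wide 95% band as support for the coefficients

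*Protocol*

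**What the plan says.** Section 11.3 names two outcomes: how many patients the model places in the top three deciles, and the proportion of those patients who are positive. For that group it expects that the "resulting population would have an oral high-risk prevalence of 8.43% (95%CI 6.68% to 10.14"%). It then tabulates 95% bounds around 8.43% for sample sizes of 100 to 500, "assuming a range of 10-50% of the study population is categorized as high-risk based on our model". The row for the planned size reads "300 8.43% 5.29% 11.57"%.

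The decision sentence follows. "A proportion of the study population with oral high-risk infection that falls within the confidence bounds in the table below, given the sample size" is said to indicate that the coefficients in the NHANES "model are reasonable estimates of risk to the study population".

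Two other sections bear on this:

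- Hypothesis 1 in 11.1 concerns the proportion positive "among individuals selected for oral rinse collection will be similar to the proportion predicted by the risk factor model".
- Sections 3.1 and 3.2 define the primary objective and outcome over the study population, as the decision sentence does.

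**The concern.** One comparison is given three denominators: the study population (the decision sentence), everyone selected for a rinse (hypothesis 1), and the top three deciles (the group the 8.43% and the table describe). Because the decision sentence shares its denominator with the primary outcome, an analyst could follow it literally and test the wrong quantity.

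The inference is a separate problem. A result inside a 95% band around a predicted value means only that the prediction was not rejected. The protocol turns this into a positive statement about the coefficients, with no margin for acceptable disagreement. The 90% power in 11.2 applies to the share of patients classified high-risk, not to this comparison.

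The end of 11.3 says the pilot will inform the estimates and models behind a future study of 60,000 screened people. An overstated conclusion about the model could carry over into that planning.

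**Working it through.** **Inputs from the protocol.** Predicted prevalence in the top three deciles 8.43%, CI 6.68% to 10.14% (11.3). Share expected to be high-risk 30%, about 300 of 1,000 (11.2: "we expect 30% of the study population to be categorized as high-risk"). Rinses from about 300 top-decile and about 59 lower-decile patients (Protocol Summary). Anticipated positives 2.5% of all patients (6.2.1). The prevalence in the lower seven deciles, p_low, is not given; I vary it from 0% to 4% as an assumption.

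**1. The table reproduces.** The bounds are p ± 1.96 × √(p(1−p)/n) with p = 0.0843. For n = 300: √(0.0843 × 0.9157 / 300) = 0.01604, and 1.96 × 0.01604 = 0.0314, giving 5.29% to 11.57%. All ten bounds agree to two decimals, so the arithmetic is sound.

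**2. Literal reading (whole study population).** If the model is exactly right, prevalence is 0.30 × 8.43% + 0.70 × p_low:

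- p_low 0%: 2.53%
- p_low 1%: 3.23%
- p_low 2%: 3.93%
- p_low 3%: 4.63%

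All are below the 5.29% bound for n = 300. Reaching it needs p_low = (5.29 − 2.53)/0.70 ≈ 3.9%. The protocol's 2.5% counts detected positives over everyone enrolled. It is below every lower bound, including 2.98% at n = 100.

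**3. Everyone selected (hypothesis 1).** The expected proportion is (300 × 8.43% + 59 × p_low)/359, which is 7.0% at p_low 0% and 7.7% at 4%. Against the n = 300 band, a correct model passes 93% to 97% of the time.

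**4. Contextual reading (top three deciles).** Exact binomial probability of landing inside the band, with the passing counts in the header:

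| True prevalence | Ratio to 8.43% | n = 100 (3–13) | n = 300 (16–34) | n = 500 (30–54) |
|---|---|---|---|---|
| 4.2% | 0.50 | 80% | 20% | 3% |
| 5.0% | 0.59 | 88% | 43% | 18% |
| 6.0% | 0.71 | 94% | 72% | 53% |
| 8.43% | 1.00 | 95% | 95% | 96% |
| 12.0% | 1.42 | 69% | 40% | 23% |
| 12.65% | 1.50 | 61% | 28% | 12% |

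At n = 300 the chance of falling outside the band reaches 80% only at about 4.2% or lower (0.50 times predicted) or about 13.2% or higher (1.56 times).

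**5. Individual coefficients.** If every patient had a prevalence of 8.43% whatever the risk score, the model would have no discrimination at all, yet the rule would still pass 95% of the time at n = 300.

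**6. Uncertainty of the benchmark.** The NHANES standard error is (10.14 − 6.68)/3.92 = 0.88 points. Combined with the sampling error of 1.60 points at n = 300: 1.96 × √(1.60² + 0.88²) ≈ 3.59, giving 4.84% to 12.02% instead of 5.29% to 11.57%.

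**7. Fixed benchmark.** The table keeps 8.43% whether 10% or 50% of patients are classified high-risk. If case mix differs from NHANES, the mean predicted risk of those patients can differ from 8.43% with the coefficients unchanged.

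**8. What an on-target result would show.** Take 25 positives among 300 evaluable rinses, and a mean predicted risk of 8.43% with the NHANES error above. Expected positives are 300 × 0.0843 = 25.3, so observed/expected is 0.99. On the log scale the variance is about (1 − 25/300)/25 + (0.88/8.43)² = 0.0367 + 0.0110 = 0.0477, standard error 0.218. The 95% CI is 0.99 × exp(±1.96 × 0.218), about 0.64 to 1.52.

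**The case against.** The best defence is that context settles the denominator. Section 11.3 defines its outcome within the top three deciles, the rows are numbers of high-risk patients, the bound is to be read at the matching sample size, and there is no row for 1,000. The authors' own 2.5% would fail every row, so they cannot have meant the whole population. This stands. A reader might infer that the rule rejects a correct model, but only the literal wording does that, and its pass rate there depends on a lower-decile prevalence the protocol does not give.

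Other points also stand:

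- A reader might see a contradiction between 30% selected in 11.3 and 6.2.1, where patients are selected "by the web-application for oral rinse sample (approximately 35.9% of patients". There is none. Section 11.3 means selection based on risk, and adding the random lower-decile sample gives 300 + 59 = 359.
- The text claims that the coefficients are reasonable estimates, not that they are proven.
- Enrolment is fixed at about 1,000, so nobody gains by recruiting fewer. The n = 100 row arises only if 10% rather than 30% are high-risk, which the comparison powered in 11.2 would probably flag.
- Case mix is examined separately in 11.3, by a chi-square test on risk deciles and by variable. A shift would be visible, although the benchmark would still not adjust for it.
- Adding the NHANES error widens the band and makes passing easier. That argues for reporting an interval, not for keeping the rule with a wider band.

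None of this repairs the decision sentence or turns non-rejection into evidence of agreement.

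**Conclusion.** The point holds on two counts. The denominators in 11.1 and 11.3 must be reconciled, because the decision sentence as written does not describe the group for which its bounds were computed. And on the sensible reading, at the planned 300 high-risk patients, a prevalence 29% below prediction passes 72% of the time and one 42% above passes 40%. With 100, half the predicted prevalence passes 80%. Passing therefore cannot carry the stated conclusion, least of all about individual coefficients.

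A reader might go further and infer that the rule lets any badly wrong model through. At n = 300 that is not supported: prevalences of about half the prediction or lower, or about 1.56 times or higher, are rejected about 80% of the time or more. The weakness concerns moderate miscalibration and wrong individual coefficients.

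The pass rates assume independent binomial outcomes and evaluable rinses from all high-risk patients. Only the whole-population figures depend on p_low, and their direction is the same for any p_low below 3.9%. This is a should-fix: what the pilot may conclude changes, but the protocol states no go/no-go decision that depends on the rule.

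**What to change.** - In 11.1(1) and 11.3, name the denominator as top-three-decile patients with an evaluable rinse (7.2.1 provides for inevaluable samples).
- Replace the fixed 8.43% by the mean NHANES-model predicted risk of the patients actually tested. Report observed over expected positives with a 95% CI that includes the NHANES error.
- Delete the statement that a value inside the bounds indicates reasonable coefficients. State instead which observed/expected ratios the CI excludes. The table can stay as an illustration of precision.
- Treat any calibration slope that uses the lower-decile rinses as exploratory only. At an assumed prevalence of 1% to 2%, 59 patients yield 0.6 to 1.2 expected positives, and the chance of none is 0.99^59 = 55% to 0.98^59 = 30%. With 1-in-12 sampling, each such positive would carry a weight of about 12.

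The cost is a change of wording and a short analysis of data already collected; the NHANES model's error must be to hand. The downside is a less favourable conclusion than a confirmed model: even an on-target result would leave a ratio of roughly 0.64 to 1.52 open.

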- Précis:** A target of 1,000 men and women aged 30-69 years will be enrolled over a 6-month period, with up to 1,200 enrollments allowed to avoid cutting off enrollment in the middle of a business day. Approximately thirty practice locations will be recruited from the 6 National Dental PBRN regions (approximately 5 practice locations per region). Approximately 40 practitioners will be recruited among the approximately 30 practice locations. Participating patients will be recruited during routine clinical visits with participating National Dental PBRN practitioners. Each practitioner will recruit approximately 25-50 patients. Patients will be provided a tablet computer on which the study will be explained, electronic consent will be obtained, patient eligibility will be assessed, an oral HPV risk factor survey will be administered, and patient selection for oral rinse collection will be determined. Based on survey responses, the top three deciles of risk (~300) and a random selection of 1 in 12 of those in the lower deciles (~59) will be selected for oral rinse collection (~359 total). An oral rinse sample will be obtained by means of a 30 second rinse and gargle with Scope™ mouthwash (or saline), expectorated into a sterile specimen collection cup, sealed and stored at 4°C. Specimens will be shipped by practice staff approximately weekly or twice a week to a central laboratory for human papillomavirus (HPV) detection. HPV results will be communicated to the dental practitioner through the study's secure web application. Patients with a high-risk oral HPV infection (anticipated to be ~25 individuals) will be offered enrollment into a prospective study inclusive of a blood draw, an oral cancer examination, and a 6-month follow-up dental visit (window: 5-9 months) with a repeat oral rinse and an electronic oral cancer risk factor survey. Patients will be compensated with a gift card for each major study procedure.
- Objectives:** The primary objective of this study is to estimate the proportion of the study population with an oral high-risk HPV infection.
- The secondary objectives of this study are to:
- (1) Evaluate the feasibility and acceptability of baseline study procedures performed by participating patients and staff;
 - (2) Measure the distribution of demographic and behavioral

characteristics associated with oral HPV infection;

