3 OBJECTIVES

3.1 Study Objectives

The primary objective of this study is to estimate the proportion of the study population with an oral high-risk HPV infection.

The secondary objectives of this study are to:

- (1) Evaluate the feasibility and acceptability of baseline study procedures performed by participating patients and staff;
- (2) Measure the distribution of demographic and behavioral characteristics associated with oral HPV infection; and
- (3) Determine compliance with and feasibility of procedures performed at a 6-month follow-up visit (window: 5-9 months), including blood draw, second oral rinse specimen collection, oral cancer screening examination, and completion of an oral cancer risk factor survey (Appendix J).

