3.2 Study Outcome Measures

The primary study outcome measure is the proportion of the study population with an oral high-risk HPV infection, which will be assessed through laboratory testing of the oral rinse specimen, recorded on a laboratory testing electronic Case Report Form (eCRF).

Secondary study outcome measures corresponding to the secondary objectives noted above will include:

- (1) The feasibility and acceptability of baseline study procedures performed by participating patient and dental office staff as assessed through:
 - a. Patients:
 - i. Electronic study summary (Appendix A): proportion of patients who agree to learn more about the study; proportion of patients who screen eligible to participate; proportion of patients who agree to the electronic consent.
 - ii. Oral HPV risk factor survey (Appendix C): acceptability of questions about risk factors ascertained in the survey.
 - b. Dental office staff:
 - i. Practitioner acceptability: Practitioners approached to participate in the study, those who agree or decline participation during the consent process, and practitioners who complete study-specific training.
 - ii. Feasibility (protocol education/training; patient recruitment; patient consent; answering questions; collecting, storing, and shipping oral rinses; distributing gift cards; providing test results).

-
- iii. Provider survey (Appendix P): ascertains acceptability (acceptability of extra time required for study procedures; comfort with study procedures; interest in participating in a future study) among practice staff.
- (2) The distribution of demographic and behavioral characteristics associated with oral HPV infection as assessed by the oral HPV risk factor survey (Appendix C) (gender; age; race/ethnicity; marital status; education; cigarette smoking; lifetime number of sexual partners) stratified by oral HPV status (laboratory testing eCRF).
- (3) The compliance with and feasibility of procedures done at the 6-month follow up visit performed by participating patients and dental office staff as assessed through:
- a. Patients:
 - i. eCRFs completed by the Regional Coordinator (RC), and will include a proportion of individuals with oral high-risk infection who: (a) enroll in the prospective study; (b) attend a 6-month follow-up; (c) undergo phlebotomy; (d) undergo ENT exam; and (e) complete the Oral Cancer Risk Factor Survey (Appendix J).

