To accomplish secondary objective (2) the distribution of the demographic and behavioral variables in the study population will be compared to the weighted distribution of the same factors in the US population per NHANES. In this analysis, the distribution of the populations into deciles of risk will be represented in an $n \times k$ table where n represents the two populations and k the deciles of risk. The distribution will be compared by chi square test with nine degrees of freedom. The distribution of each variable in the two populations will also be compared in univariate analysis. Successful completion of this pilot will therefore: (1) assess patient acceptability of the procedures; (2) provide training to study personnel and assess the feasibility of incorporating the study procedures into clinical practice; and (3) inform the point estimates and models used for sample size determination for a future larger study to ensure that the estimate of 60,000 screened individuals is appropriate.

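### The analysis assigned to secondary objective 2 never uses HPV status, so it does not deliver the by-status outcome that Section 3.2 defines; a by-status table must also respect the unequal rinse sampling

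*Protocol*

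**What the plan says.** **Objective.** Section 3.1 states objective 2 as: "Measure the distribution of demographic and behavioral characteristics associated with oral HPV infection".

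**Outcome.** Section 3.2 ties it to the oral HPV risk factor survey, lists seven variables ("gender; age; race/ethnicity; marital status; education; cigarette smoking; lifetime number of sexual partners") and requires them "stratified by oral HPV status (laboratory testing eCRF").

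**Analysis.** Section 11.3 assigns one analysis: "To accomplish secondary objective (2) the distribution of the demographic and behavioral variables in the study population will be compared to the weighted distribution" of those factors in the US population per NHANES. It cross-classifies the two populations by risk decile. "The distribution will be compared by chi square test with nine degrees of freedom". Each variable is then also compared univariately between the two populations.

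**Who has an HPV result.** The Précis selects for oral rinse "the top three deciles of risk (~300) and a random selection of 1 in 12 of those in the lower deciles", about 359 patients in all. Section 7.3.1.1 limits the rinse to patients selected by the web application, and Section 6.2.1 expects about 64.1% of patients not to be selected.

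**The concern.** The outcome needs a laboratory result for each patient it describes. The assigned analysis contrasts all enrolled patients with an external survey and needs none. Carried out exactly as written, Section 11.3 would produce no table of characteristics by HPV status, and objective 2 would go unreported.

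The gap also hides a sampling problem. HPV status is observed in a subset chosen by a risk score. Section 2.2 names age, gender, number of sexual partners and cigarettes per day as the factors associated with infection that a brief questionnaire would assess. Four of the seven outcome variables are therefore tied to selection. If whoever fills the gap simply pools the tested patients, the HPV-negative column will largely describe the selection rule. Section 11.3 intends the pilot to inform estimates and models for a larger study, so a misread table could carry forward.

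**Working it through.** **1. Outcome and analysis side by side**

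| | Section 3.2 outcome | Section 11.3 analysis |
|---|---|---|
| Patients described | those with an HPV result | all enrolled |
| Groups compared | HPV-positive, HPV-negative | study population, NHANES |
| Laboratory result needed | yes | no |
| Question answered | objective 2 | hypothesis 3 (similarity to the US population) |

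The 9 degrees of freedom confirm this reading: a table of 2 populations by 10 deciles has (2 − 1)(10 − 1) = 9. HPV status is not a dimension of it.

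**2. The plan's own design figures**

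Inputs: 1,000 enrolled, sampling fractions 1 and 1/12 (Précis), prevalence 8.43% in the top three deciles (Section 11.3).

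- Lower-decile rinses: 700/12 = 58.3 (stated about 59).
- Total rinses: 300 + 58.3 = 358.3 (stated about 359).
- Positives in the top three deciles: 300 × 0.0843 = 25.3 (stated about 25 in total).

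The figures reproduce. The top deciles alone account for the stated 25 positives, so the protocol's numbers imply a lower-decile prevalence near zero. That prevalence, q, is not stated; I take 0% to 3% as an assumption.

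**3. HPV-negative column**

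Negatives in the top three deciles: 300 − 25.3 = 274.7.

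- Unweighted share from the top three deciles: 274.7 / [274.7 + 58.3(1 − q)]. At q = 0: 274.7/333.0 = 82.5%. At q = 3%: 274.7/331.3 = 82.9%.
- Share among all enrolled negatives (weights 1 and 12): 274.7 / [274.7 + 700(1 − q)]. At q = 0: 274.7/974.7 = 28.2%. At q = 3%: 274.7/953.7 = 28.8%.

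The gap hardly depends on q.

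**4. HPV-positive column**

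Unweighted share from the top three deciles: 25.3/(25.3 + 58.3q). Weighted: 25.3/(25.3 + 700q).

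| q (assumed) | Unweighted | Weighted |
|---|---|---|
| 0% | 100% | 100% |
| 1% | 97.7% | 78.3% |
| 2% | 95.6% | 64.4% |
| 3% | 93.5% | 54.6% |

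This column depends strongly on q, and at q = 0 it is not distorted at all.

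**5. Effect on a crude association (illustration only)**

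Assume a factor present in 80% of top-decile and 30% of lower-decile patients, unrelated to HPV within each group. Its frequency in a column is 0.8 × share + 0.3 × (1 − share).

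- q = 1%, unweighted: 78.9% of positives, 71.3% of negatives; odds ratio (0.789/0.211)/(0.713/0.287) = 1.5.
- q = 1%, weighted: 69.2% and 44.2%; odds ratio 2.8.
- q = 0: positives 80% either way, negatives 71.2% unweighted and 44.1% weighted; odds ratios 4/2.48 = 1.6 and 4/0.789 = 5.1.
- q = 3%: odds ratios 1.3 and 1.7.

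In every case the unweighted crude odds ratio is nearer to 1.

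**6. Precision of a weighted table**

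- Expected lower-decile positives among 58.3 rinses: 0 (q = 0) to 1.75 (q = 3%).
- Chance of none among 59 at q = 1%: 0.99^59 = 55%.
- A single one would carry 12/(25.3 + 12) = 32% of the weighted positive column.
- Kish effective sample size of all rinses: (300 + 12 × 59)² / (300 + 144 × 59) = 1,008²/8,796 = about 116, from 359.

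**The case against.** **Objective 2 could mean factors already known to be associated with HPV.** On the Section 3.1 wording alone, an NHANES comparison would fit that reading. Section 3.2 closes it off by naming the stratifier and its source form.

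**No unweighted table is specified.** This stands. A reader might infer that the protocol commits to a distorted tabulation. It does not: it specifies no by-status tabulation at all, and Section 11 refers to a SAP that was not available here and could set weights. The distortion is therefore conditional. The mismatch between Sections 3.2 and 11.3 is not, because Section 11.3 positively assigns a different analysis.

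**The risk model is not harmed.** This also stands. A reader might infer that the sampling biases the model coefficients. Selection depends only on survey responses, so a model of HPV that properly adjusts for the selection variables is not biased by it; only crude, pooled comparisons are affected. Section 11.3 also links the β-estimates to the proportion positive among those selected as high-risk, not to the objective 2 table.

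**Not all seven variables are shown to drive selection.** Correct. Section 2.2 supports four. Race/ethnicity, marital status and education would be affected only as far as they correlate with the score.

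**Weighting is fragile here.** Also fair. With zero to about two lower-decile positives, weights of 12 give very imprecise results. Reporting by sampling stratum is a reasonable alternative, so weights should not be the only acceptable answer.

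**Conclusion.** The concern holds in two parts of different strength.

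- **Firm:** Sections 3.2 and 11.3 disagree, and the analysis assigned to objective 2 does not deliver its defined outcome. This rests on the text alone.
- **Conditional:** if the missing table were pooled and unweighted, about 83% of HPV-negatives would come from the top three deciles, against about 28% in the enrolled population, for any lower-decile prevalence from 0% to 3%. Crude associations could be attenuated; the odds ratios above rest on an assumed factor. The effect on the HPV-positive column ranges from none to large, and the protocol's own count of positives points to the low end.

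This should be fixed, but it is not critical. The objective is a descriptive secondary one in a pilot with about 25 expected positives, and the data needed are already to be collected.

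**What to change.** In Section 11.3:

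1. Relabel the NHANES comparison (decile chi-square and univariate comparisons) as the analysis of hypothesis 3.
2. For objective 2, describe each Section 3.2 characteristic by HPV status among rinse-tested patients in a way that respects the sampling. Either weight by inverse selection probability (1 and 12, or the inverse of the realised fractions) with design-based intervals, or report separately for the top three deciles and the lower deciles.
3. State that these results are descriptive, since about 25 positives are expected and few or none from the lower deciles.

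The cost is wording only. Selection is made by the web application, so the fractions are known and no data collection changes. The drawback is wide intervals when weighted, or a nearly empty lower-decile positive cell when stratified.

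### Hypothesis 3 claims similarity to the US population, but the tests that the protocol names for it are tests of difference, which cannot establish similarity

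*Protocol*

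**What the plan says.** Protocol section 11.1 opens with "This pilot study is designed to test the following hypotheses". The third hypothesis reads: "The distribution of demographic and behavioral risk factors in the study population will be similar to the US population".

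Section 11.3 gives the matching analysis under secondary objective 2. The study's demographic and behavioral variables "will be compared to the weighted distribution of the same factors in the US population per NHANES". The table is two-way, "where n represents the two populations and k the deciles of risk", and "The distribution will be compared by chi square test with nine degrees of freedom". It adds: "The distribution of each variable in the two populations will also be compared in univariate analysis". No method is named for these univariate comparisons.

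Section 11.2 contains one more test that bears on the risk distribution. It concerns the share of patients classed as high-risk, expected to be 30%, and the effect it is sized for is a shift of at least 5 points in that share: "A two-sided test of proportions with a type 1 error of 0.05 indicates that a pilot study with 1,000 individuals will have 90% power".

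Section 11.3 has one explicit agreement rule: an observed proportion inside tabulated 95% bounds means that the NHANES model coefficients are reasonable. That rule concerns the HPV-positive proportion, so it serves hypothesis 1. The protocol states no counterpart for hypothesis 3.

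**The concern.** Hypothesis 3 is a claim of similarity. A chi-square test of two distributions takes equality as its null hypothesis. Rejection is evidence against hypothesis 3. Non-rejection shows only that the data did not reveal a difference, which may reflect closeness or low power. The test therefore has no outcome that supports the claim, and its result depends on sample size as well as on how close the populations are.

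At stake is the wording of a conclusion about how representative the network's patients are. A convenience sample from about 30 dental practices could be described as similar to the US population on evidence that does not show it.

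**Working it through.** **Inputs.** From the protocol: N = 1,000; high-risk share 30%; 5-point difference; two-sided alpha 0.05; 90% power; NHANES model sample of 5,500 (all 11.2); two populations by ten deciles (11.3). Section 7.4.1 puts the NHANES participants at almost 5,000.

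Assumptions: alpha 0.05 also applies to the chi-square test, for which 11.3 gives none; the reference has 10% in each decile; the shift is spread evenly within the top three and within the lower seven deciles; both samples are simple random samples unless stated otherwise.

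**Step 1. The plan's own figures.**
- Degrees of freedom: (2 − 1) × (10 − 1) = 9, as stated.
- Power against a fixed 30%, normal approximation: Φ[(0.05 − 1.96 × √(0.30 × 0.70/1000)) / √(p1(1 − p1)/1000)].
  - At 35%: (0.05 − 1.96 × 0.01449)/0.01508 = 1.43, giving 92.4% (exact binomial 91.3%).
  - At 25%: (0.05 − 1.96 × 0.01449)/0.01369 = 1.58, giving 94.3% (exact binomial 94.1%).
- Against 5,500 NHANES subjects, two-sample test: 87.7% at 35% and 90.1% at 25%.

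The stated 90% is reproduced to within a few points. The corresponding miss rates are 5.9% to 8.7% (fixed reference, exact) and 9.9% to 12.3% (against 5,500), or about 6% to 12% overall.

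**Step 2. The same shift under the nine-degree-of-freedom test.** The critical value is 16.92.
- Fixed reference: noncentrality = 1000 × (0.05²/0.10) × (1/7 + 1/3) = 11.9. Power is 65.7%, so the miss rate is 34%.
- Against 5,500: noncentrality is 9.9 for 35% and 10.2 for 25%, with miss rates of 44% and 42%. With 5,000 reference subjects, the miss rate at 35% is 45%.
- With an assumed design effect of 2 on both samples, the noncentrality halves to about 5 and the miss rate is 71% to 72%.

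**Step 3. Dependence on sample size.** A 2-point shift against a fixed reference is rejected with 12% power at N = 1,000 and about 100% at N = 60,000, the size of the planned larger study. The populations are equally close in both cases, yet the test result would differ.

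**Step 4. What an interval rule could deliver.** The protocol gives no margin. For illustration, take ±5 points on the high-risk share, a 90% confidence interval and no true difference. Power = 2Φ(0.05/SE − 1.645) − 1.
- Fixed reference: SE = √(0.21/1000) = 0.01449; half-width 2.4 points; power 93%.
- Against 5,500: SE = √(0.21 × (1/1000 + 1/5500)) = 0.01575; half-width 2.6 points; power 87%.
- Against 5,500 with an assumed design effect of 2: SE = 0.02228; power 45%.

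**The case against.** The strongest reply is that the omnibus test is the wrong yardstick for a 5-point shift. Section 11.2 has a test sized for exactly that shift, with a miss rate of about 6% to 12%, and section 11.3 says that the number classed as high-risk informs on the distribution of risk factors. This stands as far as sensitivity goes: the 34% to 44% figure describes the chi-square test alone. It does not rescue the hypothesis, because the test in 11.2 also takes equality as its null.

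A second reply is that the protocol only says distributions will be compared, and that the objective served (3.1, secondary objective 2) is to measure a distribution. A reader might infer that a non-significant result will be declared similarity. The protocol never says so. Nor does it say that the univariate comparisons are significance tests; they could be reported as estimates. A margin or a rule of interpretation could also stand in the SAP, so its absence from the protocol is not the point here. What remains is that the protocol lists similarity among the hypotheses to be tested and itself names a difference test with its degrees of freedom.

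A reader might also infer that similarity is the condition for carrying NHANES estimates into the study of 60,000. Section 11.3 does not support that. It says that the pilot will inform the estimates and models for sizing that study, and it judges the model coefficients by the separate rule on HPV positivity.

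**Conclusion.** The point holds as a mismatch between claim and method. Neither the chi-square test in 11.3 nor the test of proportions in 11.2 can establish the similarity that hypothesis 3 asserts. The logic needs no numbers. The 34% to 44% non-significance rate only illustrates how weak a basis a non-significant chi-square would be. It rests on the assumed 5-point shift, its even spread, alpha 0.05 and no clustering; other shift patterns would give other rates, and clustering would raise it.

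The size is minor to moderate: this is a secondary objective of a pilot, and the better-powered test in 11.2 would usually expose a 5-point shift in the high-risk share.

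**What to change.** In section 11.3, base the conclusion on hypothesis 3 on estimated differences, study minus weighted NHANES, with confidence intervals. Report them for the top-three-decile share, for the decile distribution and for each risk factor. The high-risk share alone is not enough, since two populations can agree at 30% and still differ in age, sex or smoking. Use variances that allow for clustering by practice and for the NHANES survey design.

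Keep the chi-square test as descriptive and state that non-significance is not evidence of similarity.

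Then choose one of two routes:
- State a margin in advance and justify it. The 5 points in 11.2 is a candidate, but there it is a detectable difference and not a tolerance.
- Reword hypothesis 3 as descriptive.

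The cost is wording and somewhat more careful variance estimation, on the same data. The downside is that an imprecise interval must be reported as inconclusive. Under the margin route this may be common: with ±5 points and an assumed design effect of 2, power is about 45% even if the populations are identical in high-risk share.
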